12.1.3 Handling of Biological Specimens

The 10-hour fasting blood and urine samples should be sent to the designated clinical laboratory for analysis on the same day that they are collected.

Details on the collection and handling of pharmacokinetic blood samples are provided in the Procedure Manual.

12.1.4 Visual Acuity Assessment

BCVA will be measured using the ETDRS visual acuity protocol as modified by the Age-related Eye Disease Study Research Group ([AREDS report no. 8, 2001](#)). See the Procedure Manual for further details.

12.1.5 Intraocular Pressure

IOP must be measured prior to pupil dilation. Measurements will be taken using a Goldmann applanation tonometer or a hand held tonometer.

12.1.6 Optical Coherence Tomography

The approved equipment for this protocol include the following: the Stratus III (Carl Zeiss Meditec) with software version 4.0 or greater, or Cirrus (Zeiss) or Spectralis (Heidelberg). For sites using the Stratus OCT, at least 6 consecutive radial scans through the macula, each approximately 6 mm in length, will be taken according to Table 1. For sites using the Zeiss Cirrus spectral domain OCT instrument, a Cirrus Macular Cube 512 x 128 scan (128 horizontal scan lines comprised of 512 A-scans) will be required. For sites using the Heidelberg Spectralis OCT instrument images must be acquired in the Volume Scan mode with ART set to 5 (512 by 97 A scans).

Once the OCT instrument has been selected for a patient, that instrument must be used for all the study visits for that patient for the duration of the study.

12.1.7 Biomicroscopic Examination

12.1.7.1 Eyelids

Eyelids will be evaluated for pathology. If pathology is present, it will be described.

12.1.7.2 Conjunctiva (Bulbar or Palpebral)

Hyperemia

None	0	=	Normal, no flush or redness present
Trace	+0.5	=	Minimal flush, reddish color
Mild	+1	=	Mild flush, reddish color
Moderate	+2	=	Bright red color
Severe	+3	=	Deep, bright diffused redness

Edema

None	0	=	Normal, no swelling of the conjunctiva
Trace	+0.5	=	Minimal swelling of the conjunctiva, above normal, which is regional
Mild	+1	=	Mild swelling of the conjunctiva, above normal, which is regional
Moderate	+2	=	General swelling of the conjunctiva
Severe	+3	=	Extensive swelling of the conjunctiva

Subconjunctival Hemorrhage

None	0	=	No hemorrhage
Trace	+0.5	=	Flat and ≤ 1 quadrant
Mild	+1	=	Elevated and ≤ 1 quadrant, or flat and > 1 quadrant
Moderate	+2	=	Elevated and > 1 but ≤ 2 quadrants
Severe	+3	=	Elevated and > 2 quadrants

12.1.7.3 Cornea

Edema

None	0	=	Transparent and clear
Trace	+0.5	=	Trace, localized epithelial haze
Mild	+1	=	Dull glass appearance that may include fine individual microcystic changes
Moderate	+2	=	Dull glass appearance of epithelium with large number of vacuoles with or without stromal edema
Severe	+3	=	Epithelial bullae and/or stromal edema, localized or diffuse, with or without stromal striae

Superficial Punctate Keratopathy

0	=	None
+0.5	=	Trace
+1	=	Mild
+2	=	Moderate
+3	=	Severe

12.1.7.4 Anterior Chamber

For the measurements of cells and flare based on standardized uveitis nomenclature (Jabs et al, 2005), the following settings should be used:

1 x 1 mm slit	High magnification
Highest slit lamp voltage	Low ambient lighting
Illumination angle of 45 degrees	Same grader and slit lamp whenever possible

Cells

0	=	0 cells
+0.5	=	1 to 5 cells (trace)
+1	=	6 to 15 cells
+2	=	16 to 25 cells
+3	=	26 to 50 cells
+4	=	> 50 cells

Hypopyon

If hypopyon is present, it will be described and the level will be estimated in millimeters.

Flare

None	0	=	No flare seen
Faint	+1	=	Faint flare seen
Moderate	+2	=	Iris and lens details clear
Marked	+3	=	Iris and lens details hazy
Intense	+4	=	Fibrin or plastic aqueous

12.1.7.5 Iris/Pupil

The iris/pupil will be evaluated for pathology. If pathology is present, it will be described.

Rubeosis Iridis

0	=	No visible rubeosis iridis
+0.5	=	Trace visible rubeosis iridis
+1	=	Obvious vessels in 1 quadrant (≤ 90 degrees)
+2	=	Obvious vessels 2 to 3 quadrants (91 to 270 degrees)
+3	=	Obvious vessels 4 quadrants (271 to 360 degrees)

Iris Color (screening only)

Iris color will be recorded at screening using the following classification: blue, green, hazel, brown, or other (specify).

12.1.7.6 Lens

Lens Status

Lens status will be assessed as phakic, pseudophakic, or aphakic.

Cataract Assessment (phakic eyes only)

Presence and severity of nuclear, cortical, and posterior subcapsular cataract lens opacities will be evaluated by comparing biomicroscopic findings with standard photographs (refer to the Procedure Manual for further details). Grades are assigned as follows for each type of opacity:

Opacity is absent

Opacity is present, but less than standard photo #2

Opacity is present and as severe as or worse than standard photo #2

Assessment of Impact of Cataract on Visual Acuity

Assuming that lens opacities were the only vision-limiting condition present in this eye, estimate what the best-corrected distance visual acuity would be based on lens opacities. Assume an undilated pupil and indoor lighting conditions.

None
20/25 ~ 20/40
20/50 ~ 20/100
> 20/100

Posterior Capsule Assessment (aphakic or pseudophakic eyes only)

For aphakic or pseudophakic eyes, the posterior capsule will be assessed and recorded as intact (yes or no).

12.1.8 Fundus Ophthalmoscopic Examination

When possible, for consistency purposes, the same lens(es) should be used for all assessments throughout the study.

12.1.8.1 Macula

The macula will be evaluated for pathology. If pathology is present, it will be described. Note if the condition is not evaluable.

12.1.8.2 Optic Nerve

The optic nerve will be evaluated for pathology. If pathology is present, it will be described. Note if the condition is not evaluable.

Cup/disc ratio will be reported using a 0.0 to 1.0 scale according to an Armaly chart provided by Allergan. Note if the condition is not evaluable.

12.1.8.3 Vitreous

(1 x 3 mm beam in anterior vitreous) (Opremcak, 1995)

Cells

0	=	None
+0.5	=	1to10 cells
+1	=	11 to 20 cells
+2	=	21 to 30 cells
+3	=	31 to 100 cells
+4	=	> 100 cells

Note if the condition is not evaluable.

Vitreous Haze

The ophthalmologist will grade vitreous haze by viewing the optic disc and posterior retina using the following settings and by comparing the haze against a photographic standardized scale (Nussenblatt et al, 1985) according to the chart provided by Allergan.

Indirect ophthalmoscope and a 20-diopter lens

Illumination set to mid-power

Large beam

Low ambient lighting

Same grader and indirect ophthalmoscope whenever possible

The scale is categorized as follows:

0	=	No inflammation
+0.5	=	Trace inflammation (slight blurring of the optic disc margins and/or loss of the nerve fiber layer [NFL] reflex)
+1	=	Mild blurring of retinal vessels and optic nerve
+2	=	Moderate blurring of optic nerve head
+3	=	Marked blurring of optic nerve head
+4	=	Optic nerve head not visible

Note if the condition is not evaluable.

Vitreous Hemorrhage

Vitreous hemorrhage will be evaluated for severity. Indicate whether or not it is localized to the injection site.

0	=	No visible evidence of hemorrhage on fundus ophthalmoscopic exam
+0.5	=	Retinal detail is visible; trace hemorrhage is present
+1	=	Retinal detail is visible; mild hemorrhage is present
+2	=	Large retinal vessels are visible; central retinal detail is not visible
+3	=	Red reflex is visible; no central retinal detail is seen posterior to the equator
+4	=	No red reflex

Posterior Vitreous Detachment

The presence or absence of a posterior vitreous detachment will be evaluated. Note if the condition is not evaluable.

12.1.8.4 Retina

Retinal Hemorrhage

The presence or absence of a retinal hemorrhage will be evaluated. Note if the condition is not evaluable.

Retinal Tear

The presence or absence of a retinal tear will be evaluated. Note if the condition is not evaluable.

Retinal Detachment

The presence or absence of a retinal detachment will be evaluated. It will be noted if the center of the macula is detached. Note if the condition is not evaluable.

Lattice Degeneration

The presence or absence of lattice degeneration will be evaluated at screening and exit. If present, the condition will be described. Note if the condition is not evaluable.

Round (Atrophic) Retinal Holes

The presence or absence of round retinal holes will be evaluated at screening and exit. If present, the condition will be described. Note if the condition is not evaluable.

12.1.9 Fluorescein Angiography

Early and transit images will be taken of the study eye. Mid- and late-phase images will be taken of the study and nonstudy eye. Angiograms will be read by the study investigator to determine eligibility.

Electronic FA images will be collected for efficacy evaluation by a reading center.

[REDACTED]

12.1.11 Modified-ETDRS Focal Photocoagulation Technique

The laser treatment “session” should generally be completed in a single “sitting.” The photocoagulation treatment technique, as described below, is a modification of the ETDRS technique and is the treatment approach that is commonly used in clinical practice ([Modified ETDRS Focal Photocoagulation Technique \[Internet\], 2006](#)).

Burn characteristic	Direct/grid photocoagulation (modified-ETDRS technique)
Direct treatment	Directly treat all leaking microaneurysms (MA) in areas of retinal thickening between 500 and 3000 microns from the center of the macula (although may treat between 300 and 500 microns of macula if center-involved edema persists after initial focal photocoagulation, but generally not if the visual acuity is better than 20/40)
Change in MA Color with Direct Treatment	Not required, but at least a mild gray-white burn should be evident beneath all MAs
Burn size for direct treatment	50 microns
Burn duration for direct treatment	0.05 to 0.1 sec
Grid treatment	Applied to all areas with edema not associated with MAs. If FA is obtained, grid is applied to areas of edema with angiographic nonperfusion when judged indicated by the investigator
Area considered for grid treatment	500 to 3000 microns superiorly, nasally and inferiorly from center of macula 500 to 3500 microns temporally from macular center; no burns are placed within 500 microns of disc
Burn size for grid treatment	50 microns
Burn duration for grid treatment	0.05 to 0.1 sec
Burn intensity for grid treatment	Barely visible (light gray)
Burn separation for grid treatment	2 visible burn widths apart
Wavelength (grid and focal treatment)	Green to yellow wavelengths

12.2 Glossary of Abbreviations

Term/Abbreviation	Definition
ANCOVA	analysis of covariance
AREDS	Age-Related Eye Disease Study Research Group
BCVA	best-corrected visual acuity
BRB	blood-retinal barrier
CI	confidence interval
CMH	Cochran-Mantel-Haenszel
DEX PS DDS	700-µg extruded dexamethasone posterior segment drug delivery system (extruded drug outside the applicator)
DME	diabetic macular edema
DR	diabetic retinopathy
eCRF	electronic case report form
EDC	electronic data capture system
ETDRS	Early Treatment Diabetic Retinopathy Study
FA	fluorescein angiography
GCP	Good Clinical Practice
ICH	International Conference on Harmonisation
IEC	Independent Ethics Committee
IRB	Institutional Review Board
IOP	intraocular pressure
ITT	intent-to-treat (population)
IVRS/IWRS	interactive voice/web response system
MA	microaneurysms
MedDRA	Medical Dictionary for Regulatory Activities
NSAIDs	nonsteroidal anti-inflammatory drugs
OCT	optical coherence tomography
OU	both eyes
PK	pharmacokinetic
PLGA	poly (lactic-glycolic) acid
PP	per-protocol (population)
QID	4 times per day
RVO	retinal vein occlusion
SE	study eye
VA	visual acuity

Term/Abbreviation	Definition
VEGF	vascular endothelial growth factor
█	█
WHO	World Health Organization

12.3 Protocol Amendment Summary

Title: Dexamethasone Posterior Segment Drug Delivery System Versus Laser Photocoagulation in Patients with Diabetic Macular Edema

Protocol 206207-026 Amendment 1

Date of Amendment: April 2013

Amendment Summary

This summary includes changes made to Protocol 206207-026 (approved 01 September 2012). The following key changes were made 1) adding pharmacokinetic analysis; 2) modification of the study sample size.

[Redacted]

[Redacted]

[Redacted]

[Redacted]

[Redacted]

[Redacted]

[Redacted]

[Redacted]

[Redacted]

[REDACTED]

[REDACTED]

[REDACTED]

[REDACTED]

[REDACTED]

[REDACTED]

[REDACTED]

[REDACTED]

[REDACTED]

[REDACTED]
[REDACTED]
[REDACTED]

[REDACTED]
[REDACTED]
[REDACTED]

[REDACTED]
[REDACTED]

[REDACTED]
[REDACTED]
[REDACTED]

[REDACTED]
[REDACTED]

[REDACTED]

[REDACTED]
[REDACTED]
[REDACTED]
[REDACTED]
[REDACTED]
[REDACTED]
[REDACTED]

[REDACTED]
[REDACTED]
[REDACTED]

[REDACTED]
[REDACTED]

[REDACTED]
[REDACTED]

[REDACTED]
[REDACTED]
[REDACTED]
[REDACTED]
[REDACTED]
[REDACTED]

[REDACTED]
[REDACTED]

[REDACTED]
[REDACTED]

ALLERGAN

Protocol 206207-026 amendment 1

Date (DD/MMM/YYYY)/Time (PT)

████████████████████

Signed by:

██████████

Justification

██

ATC	Anatomical Therapeutic Chemical
AUC	Area under the curve
BCVA	Best corrected visual acuity
CFB	Change from baseline
CI	Confidence interval
CMH	Cochran-Mantel-Haenszel
CRT	Central retinal thickness
D	Day
DEX PS DDS	Extruded dexamethasone posterior segment drug delivery system
DME	Diabetic macular edema
ETDRS	Early treatment diabetic retinopathy study
Ecrf	Electronic case report form
FA	Fluorescein angiography
IOP	Intraocular pressure
LS	Least squares
M	Month
MedDRA	Medication Dictionary for Regulatory Activities
mITT	Modified intent-to-treat
OCT	Optical coherence tomography
OU	Both eyes
PE	Physical examination
PP	Per-protocol
PT	Preferred term
SAE	Serious adverse event
SAP	Statistical analysis plan
SD	Standard deviation
SE	Standard error
SE	Study eye
SOC	System organ class
TEAE	Treatment-emergent adverse event
VA	Visual acuity
VFQ	Visual functioning questionnaire
WHO	World Health Organization

700 µg DEX PS DDS

1. Introduction

This statistical analysis plan (SAP) details comprehensive, technical specifications of the statistical analyses of the efficacy, safety data and health outcomes outlined or specified in the final protocol of Study 206207-026 amendment 1. Specifications of tables, figures, and data listings are contained in a separate document.

Study 206207-026 is a Phase 3, multicenter, randomized, 12-month comparative study. This study is conducted to evaluate the safety and efficacy of the 700 µg DEX PS DDS compared with laser photocoagulation in participants with diabetic macular edema (DME). This is a regional multicenter Phase 3 registration trial and is conducted exclusively in China and The Philippines.

[figure not shown]
1.1 Primary Study Objectives and Design

The objective of the study is to evaluate the safety and efficacy of 700µg DEX PS DDS administered every 5 months.

Consenting participants will participate in a screening period lasting 2 to 14 days to evaluate participant eligibility. After eligibility has been determined by the investigator, participants will be randomized in a 1:1 ratio to receive:

- 700 µg DEX PS DDS every 5 months
- or
- laser photocoagulation according to the modified ETDRS protocol

The randomization will be stratified by BCVA categories at baseline (≥ 34 to ≤ 49 and ≥ 50 to ≤ 70) within each investigator site. The primary efficacy variable is average change of BCVA over a period of 12 months. The total duration of study participation for each participant is approximately 12.5 months including screening and randomization/retreatment period. Participants will attend the following 11 visits: screening visit, randomization visit, 8 assessment/retreatment visits, and study exit visit, as listed in [Table 1-1](#).

2. Analysis Populations and Data Conventions

2.1 Analysis Populations

Approximately 356 participants will be enrolled at approximately 20 sites to ensure that at least 151 participants in each treatment group complete the study. Of those, approximately 10 participants assigned to DEX PS DDS at selected sites will participate in therapeutic drug monitoring.

The following 3 populations will be used for statistical analyses: modified intent-to-treat (mITT), per protocol (PP), and safety populations.

The mITT population consists of randomized and treated participants with at least one postbaseline BCVA measurement. The mITT population will be used for all analyses except per-protocol and safety analyses. Analysis for mITT will be based on the randomized treatment regardless of the actual treatment that the participant received.

The PP population is a subset of mITT population. [REDACTED]

[REDACTED]

The safety population consists of all participants who received the study medication or had the study procedure performed on the study eye. All safety analyses will be based on the safety population using the actual treatment that the participant received.

2.2 Analysis Visit Windows

Visit windows are defined according to study days.

The analysis visit windows for efficacy and safety endpoints except total leakage area are defined as follows:

Table 2-1 Analysis Visit Definitions for Safety and Efficacy (BCVA, OCT and IOP)

Study Visit (eCRF)	Analysis Visit (Derived)	Target Day (Number of Days from Day 1)	Window (Study Days)
Day 1(Baseline)	Baseline	1	≤ 1
Month 1	Month 1	30	[2, 45]
Month 2	Month 2	60	[46, 75]
Month 3	Month 3	90	[76, 120]
Month 5	Month 5	150	[121, 165]
Month 6	Month 6	180	[166, 195]
Month 7	Month 7	210	[196, 240]
Month 9	Month 9	270	[241, 285]
Month 10	Month 10	300	[286, 330]
Month 12/Exit	Month 12	360	[331, 450]

[figure not shown]
Month is defined as 30 days.

The analysis visit windows for total leakage area are defined as follows:

Table 2-2 Efficacy Analysis Visit Definitions for Total Leakage Area

Study Visit (eCRF)	Analysis Visit (Derived)	Target Day (Number of Days from Day 1)	Window (Study Days)
Day 1(Baseline)	Baseline	1	≤ 1
Month 3	Month 3	90	[2, 135]
Month 6	Month 6	180	[136, 225]
Month 9	Month 9	270	[226, 315]
Month 12/Exit	Month 12	360	[316, 450]

Month is defined as 30 days.

In cases where multiple visits occurred within a single visit window, the last visit with non-missing data will be used.

2.3 Data Conventions

- Unless stated otherwise in specific subsequent sections, data conventions and definitions listed below will be applied to all analyses. Study duration will be calculated for each participant as:

Study duration = date of the last visit – date of the 1st study treatment + 1

- In general, study day of a visit/assessment/treatment/event/procedure (i.e., BCVA assessment, escape therapy) will be calculated as below.

If the visit date is on or after the 1st study treatment, study day will be calculated as:

Study Day = visit date – date of the 1st study treatment + 1

Day 1 is the day of the 1st study treatment

If visit date is before the 1st study treatment, study day will be calculated as:

Study Day = visit date – date of the 1st study treatment

Day -1 is the day before the 1st study treatment

- Unless otherwise specified, baseline data refer to assessments performed at the Baseline (Day 1) visit prior to the first treatment. Screening or unscheduled but prior to Day 1 visits can be used for baseline in the absence of pertinent data at the baseline visit.
- For continuous variables, descriptive statistics will include mean, median, standard deviation, 25-percentile, 75-percentile, minimum and maximum. Descriptive summary for the categorical data will be count and percentage for each category.
- The Medical Dictionary for Regulatory Activities (MedDRA) nomenclature will be used to code adverse events, biomicroscopy, and ophthalmoscopy findings.
- The Anatomical-Therapeutic-Chemical classification text from World Health Organization (WHO) Drug Dictionary will be used to code all medications for drug class and for drug name.
- All data will be listed.

700 µg DEX PS DDS

- Data after the escape therapy will be excluded from efficacy analyses and will be included in safety analyses. Since assessments (e.g., BCVA, CRT) are usually performed before any treatments (e.g., study treatment, escape therapy), data collected on the same day but prior to the escape therapy will be included in analysis.
- Due to IP recall during the study, a small number of participants have delayed Ozurdex treatment at Month 12. It is recommended that these participants can come back 2 months after the last treatment for a follow-up visit. Therefore, data collected up to day 450 will be used in efficacy analysis. However, all data during the study will be included in safety analysis.

3. Disposition and Exit Status

Disposition and exit status of enrolled participants will be summarized.

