7.2.1 Primary Efficacy Variables

The primary efficacy variable is the average change from baseline in BCVA over the 12-month study period. The average change will be computed by subtracting the baseline BCVA from the area under the BCVA curve (AUC) divided by the total follow-up time for each patient. Calculations for AUC will be based on observed data using the trapezoidal method and will include all postbaseline BCVA data for the patient from the study treatment to the last VA measurement, regardless of scheduled or unscheduled visits.

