7.2.2 Secondary Efficacy Variables

Secondary efficacy variables include: ≥ 15 letters improvement from baseline in BCVA at month 12; change from baseline in the retinal thickness based on OCT at month 12; and change from baseline in total leakage area based on FA at month 12.

Change From Baseline in Retinal Thickness Based on OCT

OCT is a laser-based diagnostic system providing high-resolution optical sections of the retina. OCT will be performed at the investigators' sites. The OCT images will be transferred to the reading center and evaluated by the retina specialists of the reading center

700 µg DEX PS DDS

for the SE. The retinal thickness (microns) in the central 1-mm macular subfield based on OCT will be assessed and analyzed as the secondary efficacy variable.

Change From Baseline in Total Leakage Area Based on FA

FA is a technique to examine the circulation of the retina using the dye tracing method. It involves injection of sodium fluorescein into the systemic circulation, and then an angiogram is obtained by photographing the fluorescence emitted after illumination of the retina. The focal and diffuse leakage area based on FA will be assessed. The total leakage area defined as the sum of focal and diffuse leakage area will be computed and analyzed as the secondary efficacy variable.

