3.2 Protocol Deviation

Protocol deviations will be captured and classified by categories in a separate document. Significant protocol deviations will be summarized for the mITT Population by treatment group.

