6.1 Exposure to Study Treatment(s)

Exposure to study treatment will be summarized by the number and percentage of participants receiving 0, 1, 2, or 3 injections for the DEX PS DDS treated group, or 0, 1, 2, 3, or 4 treatments for the laser photocoagulation treated group. The mean number of study treatments and the numbers of total study days will be calculated for each treatment group.

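### Does running Month 12 to Day 450 for recall-delayed implant participants distort the Month 12 secondary endpoints?

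*SAP*

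**What the plan says.** Protocol 7.2.2 places all three secondary variables at Month 12: a gain of 15 letters or more, "change from baseline in the retinal thickness based on OCT at month 12", and the change in leakage area. In SAP 2.2 the Month 12 target is Day 360. The window is Days 331 to 450 for BCVA and OCT (Table 2-1) and Days 316 to 450 for leakage area (Table 2-2). Repeat visits are settled by one rule: "In cases where multiple visits occurred within a single visit window, the last visit with non-missing data will be used".

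SAP 2.3 gives the reason for the long upper limit. Because of a recall, "a small number of participants have delayed Ozurdex treatment at Month 12". It continues: "It is recommended that these participants can come back 2 months after the last treatment for a follow-up visit". The consequence is then stated: "Therefore, data collected up to day 450 will be used in efficacy analysis".

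The primary variable in Protocol 7.2.1 uses BCVA data "from the study treatment to the last VA measurement, regardless of scheduled or unscheduled visits". SAP 5.1.1 computes the same area but describes its end point T in terms of month 12, early termination or escape therapy.

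Two planned summaries bear on the count. SAP 6.1 gives the "number and percentage of participants receiving 0, 1, 2, or 3 injections for the DEX PS DDS treated group" and also total study days by group. SAP 3.2 states: "Significant protocol deviations will be summarized for the mITT Population by treatment group". SAP 2.3 also says that all data will be listed and defines study day for assessments and treatments.

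**The concern.** The window has the same wording for both arms, but the reason for extending it exists only in the implant arm. If a delayed participant has values at both Day 360 and Day 420, the last-visit rule discards the on-time one. On the three secondary endpoints, some implant participants could then be read about two months later in calendar time than laser participants, and soon after a fresh implant.

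The visible text gives no number affected, no summary of the actual day of the Month 12 reading, and no analysis with a tighter common cut-off. A reader might suspect that a between-arm difference at Month 12 depends partly on late readings in one arm. There is also a wording mismatch: T in SAP 5.1.1 does not mention Day 450, although SAP 2.3 admits efficacy data up to that day.

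**Working it through.** **Windows.** With 30-day months (SAP 2.2), the target is 12 x 30 = 360, as stated. Every other internal boundary is the midpoint of adjacent targets: 45, 75, 120, 165, 195, 240, 285 and 330 in Table 2-1, and 135, 225 and 315 in Table 2-2. Day 450 is the exception and comes from the recall. Mirroring the lower half-widths would give 360 + 30 = 390 for BCVA and OCT, and 360 + 45 = 405 for leakage.

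**Timing for a delayed participant.** An implant at about Day 360 plus 2 x 30 days gives Day 420. That is 60 days after target; the window allows 450 - 360 = 90.

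| Reading | Days since last implant |
|---|---|
| As planned: implant Month 10, read Month 12 | 360 - 300 = 60 |
| Delayed implant at Day 360, read Day 420 | 420 - 360 = 60 |
| Same participant, read at Day 360 before the delayed implant (Month 5 implant the last one) | 360 - 150 = 210 |

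The extension therefore keeps the planned interval after treatment and gives up calendar alignment. A cap at Day 390 or 405 does the reverse.

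**Responder endpoint.** Arm size is 356 / 2 = 178.
- Largest effect of one participant: 1 / 178 = 0.56 percentage points.
- Assumed 2 to 10 affected, with a net responder gap between the two readings of 10 to 20 points: 10 x 2 / 178 = 0.11 up to 20 x 10 / 178 = 1.12 points.
- Standard error of the between-arm difference, sqrt(2p(1 - p) / 178): 3.18 points at an assumed p = 0.10 and 4.59 at p = 0.25.
- Ratio: 0.11 / 4.59 = 0.02 up to 1.12 / 3.18 = 0.35 standard errors.

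**Thickness and leakage.** If OCT is repeated at the return visit and the two readings differ by an assumed 50 to 100 microns, 3 to 20 affected participants move the arm mean by 50 x 3 / 178 = 0.8 up to 100 x 20 / 178 = 11.2 microns. The visible documents give no basis for a figure on leakage area.

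**Primary endpoint.** Take assumed changes from baseline of 0, 6, 7, 6, 2, 6, 7, 4, 2 and 1 letters at Days 1, 30, 60, 90, 150, 180, 210, 270, 300 and 360.
- To Day 360: trapezoid area 1542, and 1542 / 359 = 4.30 letters.
- Adding Day 420 at +7: area 1542 + 60 x (1 + 7) / 2 = 1782, and 1782 / 419 = 4.25, a change of -0.04 before rounding the averages.
- Varying Day 360 from -2 to +3 and Day 420 from +3 to +11: -0.51 to +0.36 letters per affected participant.
- With 10 of 178 affected: -0.029 to +0.020 letters on the arm mean.

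A cruder check takes the average over the added days to differ by 5 to 10 letters from the average before. The added days carry 60 / 419 = 14.3% of the weight at T = 420 and 90 / 449 = 20.0% at T = 450. With 5 to 20 affected, the arm mean then moves 0.02 to 0.23 letters.

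**The case for a change.** The strongest counter-argument is that the protocol defines these endpoints by calendar month, not by time since the last implant. On that reading the Day 360 value is the right one, and replacing it with a value closer to a dose may favour the implant. Return is only recommended, and investigators know the assignment (Protocol 9.4), so who supplies a late value is not fixed by design. The number is unstated. If 3 to 20 participants were affected and all changed status in the same direction, the implant-arm rate would move by 1.7 to 11.2 points, which at the top is not small.

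Part of this stands. There are two defensible benchmarks, and the visible tables do not show how many readings are late. The extreme case is implausible, though. Twenty participants would be 11.2% of the arm, which fits poorly with the SAP's own description, and every one would have to switch the same way. BCVA staff and reading-centre graders are masked (Protocol 5.4), so the question is timing, not biased assessment.

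The information is also less hidden than it seems. Listings of all data with study days will identify a Month 12 value read at about Day 420. Total study days by arm give a partial view. Table and listing specifications are in a separate document (SAP 1), so a missing count cannot be inferred from the SAP.

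A capped analysis would not be a neutral check. It would read some delayed participants at a longer interval after their last implant than planned. It would also need a new rule for anyone seen only after the cap, because last observation carried forward in SAP 5.2 covers only escape therapy and early termination. SAP 8.1 would then require it again for the China subgroup.

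**Conclusion.** No change is needed. The Day 450 limit is a disclosed, reasoned trade-off for an unplanned supply problem: it holds the 60-day interval from implant to reading and accepts up to 60 days' calendar difference in the nominal case. Neither choice satisfies both benchmarks, and no stated rule is shown to give a wrong result.

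The likely effect is small. It is 0.02 to 0.35 standard errors on the responder endpoint if 2 to 10 participants are affected with a net gap of 10 to 20 points, and a few hundredths of a letter on the primary with 10 affected. These sizes rest on assumed counts, gaps and responder rates, because the documents give none. Whether OCT and angiography are repeated at the return visit cannot be seen, so for thickness and leakage even the mechanism is conditional. The number of late readings by arm can be taken from the planned listings and mentioned in the report without altering the analysis.

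The wording of T is a clerical matter. Read together, Protocol 7.2.1 and SAP 2.3 and 5.1.1 lead a programmer to the last BCVA up to Day 450 and before escape therapy.
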